This integration project is entitled “Effect of the Group-based Paro Intervention on Neurobiology, Cognitive Function, and Mental well-being on older adults with dementia”. This project includes 3 sub-study, that is, study 1 “Effect of the Paro intervention on cognitive function, autonomic system, reward and attachment alternations on dementia subjects in dayward center —focusing on prefrontal cortical function, dopamine, oxytocin and heart rate variability(HRV)”; study 2 ” Exploring the interaction experience and its’ relationship with the change of mental health undergoing group-based Paro intervention on attachment-specific people with dementia: Group process analysis” ; and study 3” Effect of the Paro intervention on cognitive, executive functions and mental well-being for attachment-specific people with dementia – a pilot randomized controlled trial”. The aim is to establish evidence-based Robot-pet intervention for older adults with dementia in Taiwan.

The principal investigator (study 1 PI) of the integration project is [name] who is a Director in Department of Psychiatry, NCKU hospital, Dou-Liou and is an expert at psychiatric care, dementia and aged care. He is Assistant Professor in Department of Psychiatry, College of Medicine, National Cheng Kung University. He has more than 30 publications in psychiatric and geriatric fields obtained eight awards from Government and Association in Taiwan.

The PI of study 2 is [name], who is an advanced nurse in mental health with a master degree. She also received well-trained research skill to conduct this study. She also has many publications in Chinese and co-author paper in English. She is also a person in charge to connect between school and hospital, search papers, collect data and help analyze data.

The PI of study 3 is [name] who is an Assistant Professor in National Tainan Junior College of Nursing. The PI of integration project is expert at mental health, community care and aged care. She is working on a social robot intervention on

mental health for older adults in Taiwan for 4 years. She has competence and well-trained research skill available to conduct this integration project. She will cooperate and coordinate research matters between National Tainan Junior College of Nursing and Cheng-Kung Hospital, train research staff to conduct project, supervise progress the studies, as well as quality control during the implementation.

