(5) Study 3 will conduct in at NCKU-H Dou-Liou Branch, NCKU-H related facilities, long-term care and day care center at Tainan independent facilities. Research member from NCKU-H will recruit participants and screening the participants. PI and two Co-PI will collect data and conduct intervention. Paro will provide by NTIN, other equipment are provided by NCKU-H.

(6) Monthly meeting will be held by research team members who will discuss progress of research, difficulties, and issues at NTIN or NCKU-H.

(7) The research outcome will present, poster, or publish in conference or seminar in National Tainan Junior College of Nursing and National Cheng Kung University Hospital. The results will publish in SCI, SSCI, or TSSCI journals.

VIII. Work Projects

(1) Contact with the long-term care facilities and design a flyer for recruitment of research participants.

(2) Research assistants training, establishing standardized procedures of intervention, developing data collection steps, related knowledge of processes in Paro intervention.

(3) For research fidelity, monitoring experimental group and control group by weekly check, holding regular steering meetings to maintain the quality and consistency of program implementation.

(4) Conduct data collection by blood examination, HRV measurement and psychologically testing of FTT.

- (5) To submit the manuscript to international conferences and health-related journals.
- (6) To submit the final report for the project.

IX. Expected the contribution of the Research

This study will thoroughly examine the effect of Paro intervention on Biomarkers (oxytocin level, dopamine), HRV and psychological well-being for specific attachment orientation older adults with dementia. This is the first study we know of to utilize a rigorous research design to examine the effect of intervention and explore the relationship between different attachment orientation older people and Paro. The findings of this study will provide strong evidence and advance knowledge of the mechanism of Paro intervention in LTC of Taiwan and be able to link this result to international studies. The findings of the research will publish in international journals.

X. Expected Contribution of Research to Personnel

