This is a repeated measures study that is a pilot randomized controlled trail, four parallel groups, and double-blind design. It is used to examine the effects of Paro intervention on cognition, executive functions, and mental well-being for specific attachment older adults with dementia at before, during and after the intervention. A mixed between-within subjects analysis of variance design will be used to assess the immediate effects of the 6-week Paro intervention on cognitive, executive and three mental well-being related variables for different attachment orientations of older adults living LTC facilities. Outcomes of interest measures will include dopaminergic activities variations by FTT and HRV changes at three time points: before the intervention (T0), middle of intervention (week-3, T1), the end of intervention (week-6, T2), and 1 month after the intervention (T2). Furthermore, the change of oxytocin level will be assessed at baseline and the end of the intervention.

The purpose of this study is to examine the effect of Paro intervention on neurobiologically changes for older adults with dementia in LTC. The research design is shown in Table1.

Table 1 Research design for Paro intervention

Group	Subgroup	T0	Intervention	T1	T2	T3
Security	Experiment	O ₁	X	O ₂	O ₃	O ₄
	Control	O ₁		O ₂	O ₃	O ₄

Experiment group: Paro intervention; Control group; O₁: Baseline; O₂: Week 3; O₃: Week 6; O₄: Week 10

4. Sample size, Sampling, Settings, and Participants Recruitment

There are 120 participants will be recruited into this pilot randomized controlled trial from LTC facilities in southern Taiwan. Older adults will be randomly assigned to four groups: experimental group or control group. The purpose of sampling will be used to allocate 60 participants either to the experimental group or the control group using computer generated sampling. Contact has been made with the Directors of the LTC facilities who have expressed their interest in being involved in the study. Directors will invite older adults who meet the inclusion criteria to participate in this study.

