The inclusion criteria of elderly participants will be: (1) aged 65 years or over; (2) Mild to moderate dementia (3) an ability to communicate in Mandarin or Taiwanese; and (4) has been living in the LTC facility at least 3 months. Older adults who: (1) have severe difficulty in communication; (2) are totally dependent on carers for daily activity; (3) have a diagnosed infectious disease, severe dementia, and severe mental illness such as schizophrenia and delusional disorder, will be excluded from the study.

5. Intervention

Participants in the experimental group will receive a group (6-8 people as a group) , facilitated, and 30-minute weekly session Paro intervention for 6 weeks. The control group will receive care as usual activities, such as painting, drawing, and craft, which are provided by each facility.

6. Paro

Paro (Personal Assistive Robot), was developed by [name] in Japan. It has the appearance of a baby harp seal; the current version (V9) weighs 2.5 kilograms and is approximately the size of a new-born baby. Paro is equipped with an array of tactile sensors that monitor sound, light, temperature and touch via artificial intelligence software. Paro can show human-like emotional reactions when it feels surprised, happy, or angry, and it will cry when it is neglected or not receiving sufficient attention.

In this study, Paro will be used as a Robot-pet companionship intervention with the aim to improve mental health in terms of different attachment orientations. Robot-pet companionship interventions are based on human-animal interactions aimed at providing physiological, psychological, and social benefits (Robinson et al., 2015; Chang et al., 2013; Cohen-Mansfield et al., 2010; Shibata et al., 2004).

Figure 1. The images of Paro

7. Procedure of interaction records

Participants in experimental groups will receive a group, facilitated, 30-minute weekly session of Paro intervention. A trained research assistant (RA) give the Paro to the participants at the start of each session, repeating the same introductory script each time. The RA facilitate the participant interact with the Paro during the intervention, after 30 minutes RA will use the same ending script to end the session and goodbye to participants.

8. Outcome measures

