The process and outcome of measurement will be blinded and assessed by another RA at four time points: baseline (T0), Week 3(T1), Week 6 (T2), and 1 month after the end of intervention(T3). The primary outcomes are oxytocin level, FTT results and HRV tests.

Table 2 Measurement time points and measurements

Instrument	Week-0 (T0)	Week-3 (T1)	Week-6 (T2)	Follow-up (T3)
Demographics/disease	√			

information				
Outcome measure				
-oxytocin level	√		√	
-FTT	√	√	√	√
-HRV	√	√	√	√

Note. √, collect data; FTT: finger tapping test HRV: heart rate variability

(1) Demographic data

Participants’ demographics such as age, gender, education level, religion, number of children, and previous pet ownership will be collected. Disease-related information will include the length of stay in the LTC, type of depressive disorder, any other chronic disease, a medication audit including antidepressants and other medications, and Barthel index of Activities of Daily Living.

(2) Oxytocin measurement

Blood samples for the oxytocin assay were collected from the antecubital vein into pre-chilled 5 ml EDTA tubes with 250 KIU of aprotinin, and refrigerated until processing. Plasma was isolated by centrifugation at $1800 \times g$ for 15 minutes at 4°C and stored in aliquots at -70°C. The oxytocin immunoreactivity level was quantified in duplicate using a commercial oxytocin ELISA kit (Enzo Life Sciences, NY, USA, formerly Assays Designs, MI, USA).

(3) Finger tapping test

The FTT consists of tapping with the index finger on a computer mouse as many times as possible within 10 s. The test was repeated three consecutive times and performed randomly across subjects, and the order was kept constant in each subject at each session. The average number of taps was then calculated

(4) HRV measurements

ANS activity. A full 20-minute period of recumbent acclimatization in a quiet room that was maintained at a comfortable temperature (25–27°C) preceded the cardiovascular measurements, which started at 10 AM. Subjects were asked to relax and breathe normally to avoid hyperventilation. Cardiac autonomic function was

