The aims of this study is to examine the effect of the Paro intervention on cognitive, executive functions and mental well-being for older people with dementia.

2. Objectives

- (6) To examine the effect of Paro intervention on cognitive and executive functions for older people with dementia.
- (7) To examine the effect of Paro intervention on depression for older people with dementia.
- (8) To examine the effect of Paro intervention on loneliness for older people with dementia.
- (9) To examine the effect of Paro intervention on mental well-being for older people with dementia.

3. Research design

This is a repeated measures study that is a randomized controlled trial, four parallel groups, and single-blind design. It is used to examine the effects of Paro intervention on cognition, executive functions, and mental well-being for older adults with dementia at before, during and after the intervention. A mixed between-within subjects analysis of variance design will be used to assess the immediate effects of the 6-week Paro intervention on cognitive, executive and three mental well-being related variables for different attachment orientations of older adults living LTC facilities. Outcomes of interest measures will include cognitive and executive functions, and depression, loneliness, and mental well-being at three time points: before the intervention (T0), middle of intervention (week-3, T1), the end of intervention (week-6, T2), and 1 month after the intervention (T2). Secondary outcome is interest in the impacts of the Paro intervention on psychological outcomes for different attachment style of older adults with dementia. The Revised Adult Attachment Scale Chinese version (RAAS-C) will be used to classify the attachment types of the elderly. A sub-group analysis will be conducted to further understand the changes in the physical and mental health of the elderly with different attachment types after receiving Paro intervention.

The purpose of this study is to examine the effect of Paro intervention on cognitive, executive, depression, loneliness, and mental well-being depression and loneliness for

older adults with dementia in LTC. The research design is shown in Table 1.

Table 1 Research design for Paro intervention

Group	T0	Intervention	T1	T2	T3
Experiment	O ₁	X	O ₂	O ₃	O ₄
Control	O ₁		O ₂	O ₃	O ₄

4. Sample size, Sampling, Settings, and Participants Recruitment

The same with study 1.

5. Intervention

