Participants in the experimental group will receive a group (6-8 people as a group), facilitated, and 30-minute weekly session Paro intervention for 6 weeks. The control group will receive care as usual activities, such as painting, drawing, and craft, which are provided by each facility.

6. Procedure of interaction records

Participants in experimental groups will receive a group, facilitated, 30-minute weekly session of Paro intervention. A trained research assistant (RA) will give the Paro to the participants at the start of each session, repeating the same introductory script each time. The RA facilitate the participant interact with the Paro during the intervention, after 30 minutes RA will use the same ending script to end the session and goodbye to participants.

7. Outcome measures

The process and outcome of measurement will be blinded and assessed by another RA at four time points: baseline (T0), Week 3(T1), Week 6 (T2), and 1 month after the end of intervention(T3). The primary outcomes are global cognitive function and executive functions. The Mini-Mental State Examination (MMSE) will be used to assess participants' global cognitive function. The executive functions include two components such as working memory (WM) and response inhibition, which will use computerized tasks to assess the changes of executive functions for order adults before and after intervention. Working memory will be assessed using verbal WM and visuo-spatial WM tasks. Response inhibition will be assessed employing color word stroop

(CWS), stop signal (SS), and go/no-go (GNO) tasks. The secondary outcome measures are loneliness (UCLA version-3), Depression (GDS-SF), and Mental well-being (WEMWBS).

Table 2 Measurement time points and measurements

Instrument	Week-0 (T0)	Week-3 (T1)	Week-6 (T2)	Follow- up (T3)
Demographics/disease information	√			
RAAS-C	√			
Outcome measure				
-MMSE	√	√	√	√
-Executive Functions	√	√	√	√
-Loneliness (UCLA)	√	√	√	√
-Depression(GDS-SF)	√	√	√	√
-Mental well-being (WEMWBS)	√	√	√	√

Note. √, collect data; MMSE; executive function; UCLA, the University of California Los Angeles Loneliness Scale version 3; GDS-SF, Geriatric Depression Scale - Short Form; WEMWBS, Warwick-Edinburgh Mental Well-being Scale.

(1) Demographic data

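### Section VII gives Study 3 data collection and Paro delivery to the same investigators, while the Methods assign these to two separate research assistants and promise blinded assessment

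*Combined protocol and SAP*

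**What the plan says.** Section VII (Integration of resource), item (5), deals with Study 3. After assigning recruitment and screening to hospital staff, it says: "PI and two Co-PI will collect data and conduct intervention".

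The Methods name other people for both tasks.

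- Delivery. Study 3, I.6 (Procedure of interaction records): "A trained research assistant (RA) will give the Paro to the participants at the start of each session". The same RA facilitates and closes the session with a script. Study 1, II.7 has nearly the same wording: "A trained research assistant (RA) give the Paro to the participants at the start of each session".
- Assessment. Study 3, I.7 and Study 1, II.8 (both Outcome measures) share one sentence: "The process and outcome of measurement will be blinded and assessed by another RA at four time points". Those points are T0, T1, T2 and T3.

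Study 3, I.7 also says: "The primary outcomes are global cognitive function and executive functions". Global cognition is measured with the MMSE. The secondary outcomes are UCLA loneliness, GDS-SF and WEMWBS.

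The blinding label varies. Study 3, I.3 has "four parallel groups, and single-blind design", and the Study 1 and Study 3 abstracts also say single-blind. Study 1, II.3 has "four parallel groups, and double-blind design". No label names the blinded party. (The number of groups in these phrases is a separate matter.)

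**The concern.** Anyone who conducts the Paro sessions knows who received Paro and cannot be a blinded assessor of those participants. Participants also know whether they attend Paro sessions or the facility's usual activities, so the protection against biased measurement rests largely on the outcome assessor. If staff worked from item (5) rather than the Methods, that protection would go for every measure that depends on how the examiner prompts or scores. One of these is a primary outcome. Study 3, section II records that the team expects a positive effect, which is one more reason to keep the rating in other hands. A rater shift that follows treatment arm looks like a treatment effect, and no later analysis can separate the two.

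**Working it through.** The plan states no figure on this point, and its sample size of 120 comes with no effect size, SD or power to reproduce. The check is mainly a comparison of texts, followed by an illustration.

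**Step 1. Roles side by side (Study 3).**

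| Task | Section VII (5) | Methods, I.6 and I.7 |
|---|---|---|
| Conducts sessions | PI and two Co-PIs | Trained RA |
| Collects outcome data | PI and two Co-PIs (data not further specified) | A second, blinded RA |

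The texts disagree on both rows. Study 1 draws on the same 120 participants and its Methods match the right-hand column. Item (5) itself is written for Study 3 only.

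**Step 2. Does the text confine the investigators' data to something harmless?** Study 3, Table 2 lists demographics and disease information, RAAS-C, MMSE, executive functions, UCLA, GDS-SF and WEMWBS. Item (5) does not limit itself to the first two. Group climate and satisfaction belong to Study 2, and item (5) is about Study 3. The harmless reading is possible but unstated.

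**Step 3. Which outcomes would be exposed?**

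- Exposed: the MMSE, which an examiner gives and scores, and verbal working memory, which uses slides and a total built from a mark per correct recall.
- Exposed if given by interview: UCLA, GDS-SF and WEMWBS. The mode is not stated; the Work Projects list under Study 3 speaks only of questionnaires.
- Less exposed: visuo-spatial working memory, stop-signal and go/no-go, whose results the computer displays, and oxytocin, a laboratory assay in Study 1.

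**Step 4. What a rater shift would do to an exposed outcome.** Inputs from the plan: 60 per arm (Study 1, II.4, adopted by Study 3) and a 0.05 significance level (Study 3, I.8; taken as two-sided, which the plan does not state). Assumed, because the plan gives no value: a systematic shift of b SD toward Paro, with no true effect.

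The test is a two-sample t-test with 60 + 60 − 2 = 118 degrees of freedom and critical value 1.980. The noncentrality is δ = b / √(2/60) = 5.477 b. The false-positive rate is P(T > 1.980) + P(T < −1.980), with T noncentral t.

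| b (SD) | δ | Upper tail | Lower tail | False-positive rate |
|---|---|---|---|---|
| 0 | 0 | 2.5% | 2.5% | 5.0% |
| 0.1 | 0.548 | 7.8% | 0.6% | 8.4% |
| 0.2 | 1.095 | 19.1% | 0.1% | 19.2% |
| 0.3 | 1.643 | 37.1% | 0.0% | 37.1% |

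The normal approximation, 1 − Φ(1.96 − δ) + Φ(−1.96 − δ), gives 8.5%, 19.5% and 37.6%, which agrees closely.

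**The case against.** The best defence is that item (5) is one line in a list of sites, equipment and contributions, whereas the Methods, which staff would be expected to follow, already separate the person who delivers from the person who assesses. On that view this is a drafting slip. It stands in part: the intended safeguard is in the plan, and the point is a contradiction to be removed, not a missing safeguard. But nothing says that the Methods take precedence, and item (5) is an explicit assignment of work.

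It can also be said that the investigators might collect only baseline descriptors, or divide the two tasks among themselves. The text neither says this nor rules it out.

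The illustration is open to criticism too. The shifts have no source in the plan. The test uses one time point, while Study 3, I.8 plans a covariate-adjusted mixed model, and clustering within Paro groups of 6 to 8 is ignored. All of this stands, so the percentages show sensitivity and do not estimate this trial's risk.

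A reader might infer more than the documents support:

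- That the investigators do run the sessions and rate the outcomes. This holds only under item (5).
- That the Study 2 PI rates outcomes, because section V (Work frame) has this person "search papers, collect data and help analyze data". That is a general list of duties. It mentions neither running sessions nor rating Study 3 outcomes, and Study 2 follows the experimental group only.
- That assessor blinding is the only blinding open to this design. The analyst could be blinded as well.
- That every outcome is affected. Step 3 shows otherwise.

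**Conclusion.** The contradiction is real and unresolved. Section VII (5) conflicts with the Methods of Study 3 on who delivers the sessions and on who collects outcome data, and the Study 1 Methods side with the latter. If item (5) were followed, the single-blind claim would not hold for the MMSE and verbal working memory, nor for UCLA, GDS-SF and WEMWBS if they are given by interview. For an affected outcome, assumed shifts of 0.1, 0.2 and 0.3 SD would take the false-positive rate from 5% to about 8%, 19% and 37%, under the simplifications given above. The documents do not show that unblinded rating will occur, or how large any shift would be. The textual conflict is certain and the bias is conditional. The plan should be corrected before data collection starts.

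**What to change.** 1. Reconcile section VII (5) with Study 1, II.7 and II.8 and Study 3, I.6 and I.7, so that one statement says who delivers the sessions and who assesses. Merely rewording item (5) so that the investigators deliver would leave the conflict with the Methods over delivery in place.
2. State that nobody who delivers, facilitates or attends Paro sessions collects outcome data at T0 to T3. This also covers the group observers who rate group climate in Study 2.
3. State that all outcome assessments are done by the separate RA already named in the Outcome measures sections, who attends no sessions and has no access to the allocation list.
4. Use one blinding label throughout, changing Study 1, II.3 or the other places as needed, and name the outcome assessor as the blinded party.

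The cost is a few sentences and a division of duties among staff already in the plan. No new post is needed. The practical price is that people who work in the sessions cannot stand in for the assessor.

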Participants' demographics such as age, gender, education level, religion, number of children, and previous pet ownership will be collected. Disease-related information will include the length of stay in the LTC, type of depressive disorder, any other chronic disease, a medication audit including antidepressants and other medications, and Barthel index of Activities of Daily Living.

(2) The Chinese version of Mini-Mental State Examination (MMSE)

The Mini-Mental State Examination (Folstein, Folstein, & McHugh, 1975) is a widely used tool that screens for levels of cognitive impairment, using the concepts of orientation, registration, attention and calculation, recall, and language. The MMSE has been translated into Chinese with small modifications based on the sociocultural differences of the Chinese population, and has been utilised as a dementia screening instrument for epidemiological studies (Zhang et al., 1990). The MMSE has good internal consistency with a Cronbach alpha of .91 (Marioni, Chatfield, Brayne, & Matthews, 2011). In a previous study, the MMSE has shown good sensitivity of 78.4% and a specificity of 87.8 % in primary care (Mitchell, 2008). The Cronbach alpha was .83 to .84 in older Taiwanese populations (Chung, Chiou, & Chou, 2009; Lou, Dai,

Huang, & Yu, 2007). The MMSE score ranges from 0 to 30. In general, a cut-off point higher than 24 indicates normal cognition; 20–23 mild cognitive impairment; 10–19 moderate cognitive impairment; and 0–9 severe cognitive impairment. In this study, the cut-off point was based on a study by Zhang et al. (1990) in which the level of cognitive impairment varies according to educational level: 17/18 for older people without formal education, 20/21 for those with 1–6 years of education (primary school), and 24/25 for participants with more than six years of education (middle school or higher) in Chinese older adults.

(3) Core components of executive functions- WM and response inhibition

The two core executive functions, WM and inhibition, were assessed using computerized tasks. Working memory was assessed using verbal WM and visuo-spatial WM tasks. Response inhibition was assessed using CWS, SS and GNG tasks. All older adults with dementia will be individually tested in a quiet room. The order of task administration is the same for all participants and they will receive a practice session prior to all the tasks. A period of rest is given between two tasks.

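### The baseline disease list names type of depressive disorder but not dementia type or source of diagnosis, and baseline MMSE, the only severity proxy, is tied neither to eligibility nor to the model

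*Combined protocol and SAP*

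**What the plan says.** Study 1, II.4 makes "Mild to moderate dementia" an inclusion criterion and excludes people who "have a diagnosed infectious disease, severe dementia, and severe mental illness such as schizophrenia and delusional disorder". It attaches no instrument, cut-off or diagnostic source to either degree of dementia. Under Integration of resource, item (5), "Research member from NCKU-H will recruit participants and screening the participants"; no screening tool is named there.

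The baseline disease items are in Study 1, II.8(1): "Disease-related information will include the length of stay in the LTC, type of depressive disorder, any other chronic disease", then "a medication audit including antidepressants and other medications, and Barthel index of Activities of Daily Living". Study 3, I.7(1) repeats the list word for word. Depression is not an entry criterion in any of the three sub-studies.

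Study 3, I.7 and its Table 2 schedule MMSE at T0, T1, T2 and T3. Study 3, I.4 takes its sample from Study 1, so MMSE is available for the same 120 people. Study 3, I.7(2) gives general bands of 20–23 for mild, 10–19 for moderate and 0–9 for severe cognitive impairment. It then says that this study uses education-specific cut-offs of 17/18, 20/21 and 24/25.

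Study 3, I.8 holds the model for oxytocin, FTT and HRV. It gives age and education as example covariates and leaves the list open.

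**The concern.** The one disease whose type is to be recorded is not the disease that defines the population. A reader of the results would want to know which dementias were enrolled, how each was diagnosed and whether the arms were alike. The plan lists no data that would answer this.

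It matters more here than in a trial with questionnaire outcomes only, for three reasons.

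- FTT and HRV are primary outcomes in Study 1, and the protocol reads tapping as a measure of dopaminergic activity. A dementia with motor or autonomic involvement bears on what those outcomes mean.
- Study 1 objectives (4) and (5) concern associations of the biomarkers with cognition and with group process. Randomisation does not protect such associations from a common cause such as dementia type.
- Study 1, V.2(2) recruits the control and experimental groups on different levels of a facility. If levels sort residents by care need (an assumption; the documents do not say), the arms could differ in type or stage by more than chance.

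**Working it through.** The plan gives no power calculation, effect size or SD, so there is no figure of its own to reproduce. The check has two parts.

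**1. What is recorded**

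| Item | Where | Dementia type or source? | Dementia severity? |
|---|---|---|---|
| Length of stay | II.8(1), I.7(1) | no | no |
| Type of depressive disorder | same | no | no |
| Any other chronic disease | same | only incidentally | no |
| Medication audit | same | only incidentally | no |
| Barthel index | same | no | function only |
| MMSE at T0 | Study 3, Table 2 | no | proxy |

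None of the five disease items names dementia type, stage or diagnostic source. One severity proxy exists, but no text links it to the inclusion criterion. The two sets of MMSE figures also do different jobs: the bands separate mild from moderate, and the education-specific cut-offs do not.

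**2. What the gap costs the arm comparison**

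From the plan: 60 per arm and a 0.05 level (two-sided assumed). Everything else below is an assumption.

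*Detectable difference at 80% power.*
- Unadjusted: (1.960 + 0.842) × √(2/60) = 0.511 SD.
- With a covariate explaining a share R² of outcome variance: 0.511 × √(1 − R²). For R² = 0.10, 0.20 and 0.30 this is 0.485, 0.457 and 0.428.

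*The same with the T0 outcome value already in the model.* Let r be the T0–T2 correlation, and let the dementia covariate explain R² of the outcome at both times. The total explained share is (r² + R² − 2rR²)/(1 − R²).
- For r = 0.7 and R² = 0.20: (0.49 + 0.20 − 0.28)/0.80 = 0.5125, against 0.49 without the covariate. The detectable difference goes from 0.511 × √0.51 = 0.365 to 0.511 × √0.4875 = 0.357.
- Over r = 0.5 to 0.8 and R² = 0.10 to 0.30, the added share is 0.004 to 0.107. The largest change in detectable difference is from 0.443 to 0.410 (r = 0.5, R² = 0.30).

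*Chance imbalance in type.* Suppose 10–20% of the 120 (12 to 24 people) have a dementia with motor involvement and tap 1 SD slower. The T0 variance of FTT is multiplied by 1 + p(1 − p), which is 1.09 at p = 0.10 and 1.16 at p = 0.20. The chance of a split of 1:2 or worse under 60:60 allocation is hypergeometric.

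| Such people | P(1:2 or worse) | T0 shift at exactly 1:2 |
|---|---|---|
| 12 (4 against 8) | 36% | 4/60 = 0.07 SD |
| 18 (6 against 12) | 20% | 6/60 = 0.10 SD |
| 24 (8 against 16) | 11% | 8/60 = 0.13 SD |

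Ordinary sampling error of an arm difference is √(2/60) = 0.18 SD, larger than any of these shifts. A constant offset also cancels from a pre–post difference, which is what Study 3, I.8 plans to test.

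**The case against.** The strongest reply is that the gap is narrower than it looks.

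- **Severity is measured.** MMSE at T0 covers the same sample, and bands are printed. This stands as far as it goes. But MMSE is not tied to criterion (2), is not a diagnosis, and says nothing about type.
- **The list is a summary.** It says what the information will include. The case report form and screening log are not in the documents, and chronic disease or medication entries could reveal Parkinson's disease or anti-dementia drugs. That is possible but not planned, and incidental capture would not be complete for every participant.
- **The covariate list is open.** Baseline MMSE is not ruled out. It is not named either.
- **Randomisation and T0 values protect the comparison.** This largely stands for the arm effect, as the working shows. It does not reach the association objectives, or any systematic difference between levels of a facility.

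A reader might infer that eligibility cannot be documented at all, or that variation due to dementia cannot be adjusted for. The documents support neither: baseline MMSE offers a usable severity record and covariate, and T0 values absorb much of the stable variation. Nor do they show that type is a main source of variation in tapping or HRV, since they give no figure for it. It would also go too far to say that stage at entry is lost for good; T0 MMSE covers it in part, and a charted diagnosis can usually be found later.

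**Conclusion.** The point holds as a gap in description and definition. The list names the wrong disease for this population, dementia type and diagnostic source are not planned data, and the single severity proxy is not connected to the entry criterion or to the analysis. The trial could therefore not say reliably which dementias it studied or check arm balance on type.

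It is not a source of material bias in the randomised comparison. The precision at stake is small once T0 values are in the model: 0.365 to 0.357 in the central example, and at most 0.443 to 0.410 over the range tried. An exact 1:2 imbalance on the assumed figures moves the T0 difference by 0.07 to 0.13 SD. These sizes rest on assumed prevalence, slowing, R² and T0–T2 correlation, and the documents supply none of them. The case for the change rests on the missing record, the reading of FTT as dopamine, and the association objectives.

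**What to change.** 1. In Study 1, II.8(1) and Study 3, I.7(1), replace type of depressive disorder with dementia type and source of diagnosis, taken from the chart. Keep depressive disorder as a yes/no comorbidity and add parkinsonism as another.
2. Tabulate these by arm together with baseline MMSE.
3. In Study 1, II.4, state which recorded measure documents the mild-to-moderate criterion. If it is MMSE, say which of the two sets of figures in Study 3, I.7(2) applies.
4. In Study 3, I.8, name the T0 value of the outcome and baseline MMSE as covariates. Add dementia type as a sensitivity adjustment for FTT and HRV only.

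The cost is a form edit and one chart look-up per participant. Some charts will give no type, so an unspecified category is needed. With small subtypes among 120 people the adjustment for type may gain little, which is why it belongs in a sensitivity analysis and not in the main model.
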